1.14 Will participants be randomized?

Yes

1.15 Will any of the following be used to collect information from the participant or others?

- Screening questions or screening/eligibility questionnaires
- Surveys
- Questionnaires
- Stimuli
- Any other written assessments

Yes

Attachment Name	Category	Version	Date Attached
Post-Intervention survey.docx	Subject Data Collection Instruments	1	01/07/15
Baseline survey.docx	Subject Data Collection Instruments	1	01/07/15
Narrative_6moFollowupSurvey.docx	Subject Data Collection Instruments	1	10/29/15
Follow-up survey-1 (1) (2).docx	Subject Data Collection Instruments	5	10/29/15
Narrative_12moFollowupSurvey (5).docx	Subject Data Collection Instruments	6	06/27/16

1.16 Does this project involve creating any audio, video, or photographs?

No

1.17 Does the study include any form of deception (e.g., providing participants with false information, misleading information, or withholding information about certain study procedures)?

Examples:

- Procedure includes a cover story that provides a plausible but inaccurate account of the purposes of the research.
- Participants will be provided with false information regarding the particular behaviors of interest in the research.
- Procedures include a confederate pretending to be another participant in the study.
- Participants will be told that the research includes completion of a particular task, when in fact, that task will not be administered.
- Study is designed to introduce a new procedure (or task) that participants are not initially told about.

- No
- 1.18 Indicate any payments or reimbursements to participants (check all that apply)
 - Check
- 1.19 Does this study have a plan to have an individual or committee review combined data from all participants on a periodic basis (such as summary or aggregate safety and/or efficacy data)?

No
- 1.20 What have you done to minimize any risks?
 - No foreseeable risks
- 1.21 What are the potential benefits related to this project for:
 - the participant (if any)
 - benefits to society (if any)

Participants may or may not benefit from being in this study. Participants may gain knowledge of colorectal cancer and screening options.
- Our results may change how CRC screeners' narratives are valued, used, and potentially tailored for different audiences to promote CRCS among non-adherent adults. We hope that, in the future, other people might benefit from this study because we will learn better ways to present information to educate and motivate adults to get screened for colon cancer.
- 1.22 Provide a summary of the analysis methods you will use, including, if applicable, the data points or outcomes you will analyze.

Participants assigned to study arms are expected to be equivalent on baseline measures; any differences will be included as covariates in analyses. We also will test for differential loss to follow-up, and compare results from intent-to-treat vs. complete-data analyses. To test Aim 1 hypotheses, we will conduct analyses of variance or covariance in SPSS, as appropriate. Baseline intention will be included as a covariate of later intention. Planned contrasts will compare (1) the information only vs. the pooled narrative conditions, and (2) survivor vs. screener narratives. We chose intention as the main outcome in this pilot study because it is a necessary determinant of CRCS behavior. We will also examine steps to CRCS (e.g., using or seeking CRCS information, discussing CRCS with others) as important intermediate outcomes of CRCS adherence. For Aim 2, to test indirect effects of narratives and provide empirical support for our conceptual model, we will use structural equation modeling (SEM) with Mplus software consistent with our past work. We will use recommended criteria for assessing model fit and statistical tests for identifying the magnitude and significance of multiple mediators (indirect effects). SEM can parsimoniously evaluate multiple mediators and outcomes in a single model. To test our conceptual model, we will examine message elaboration and CRCS determinants as mediators (from the Post-intervention Survey) of the effect of narratives on intentions and behaviors (from the Follow-up Survey). We propose to use manifest variables and we will create exogenous dummy variables to compare study groups. We expect stronger

effects of study condition on mediators than on outcomes and are particularly interested in differences in perceived risk, worry, and prevalence of CRC, affective reactions to narratives, and defenses. For Aim 3, two-way interactions between study condition and individual characteristics will be explored using GLM analyses in SPSS for mediators and outcomes. Post-hoc group comparisons and interaction plots will be used to describe any significant associations. We are especially interested in noting any differences in narrative effects by gender or race to address the need for stratified interventions or analyses in a future R01.

- 1.23** Provide the rationale or power analysis to support the number of participants proposed to complete this study.
Using post-intervention intention as a main outcome for Aim 1, assuming a mean score of 3.5 and a standard deviation of 1.0 on a 1-5 scale, there is >80% power to detect a 0.3 mean difference between survivor vs. screener narratives (Hyp2) with a sample size of 360 (120 per condition) at $p < 0.05$. Thus, we propose to recruit 500 participants (~167 per condition) during the 2-year study to provide sufficient power for any loss to follow up (<20%). Assuming 400 participants provide complete data, we can test our conceptual model (Figure 1) using structural equation modeling. We will have sufficient power (>.80) to detect small associations ($\beta \geq .19$) with mediators, and indirect effects as small as $\alpha\beta \geq .07$ as statistically significant.
- 1.25** Will any data from this project be stored for use in future research studies?
No
- 1.26** Does this project involve the collection or use of biological samples?
No
- 1.27** Are you requesting institutional certification to contribute human data or samples to a repository or database for broad sharing (public or restricted access)?
No

2. Participants

- 2.1** Will there be any adult participants?
Yes
- 2.1.a** How many adult participants do you expect to consent or enroll under a waiver for this project?
600
- 2.1.b** What is the age of the youngest adult participant?
50.0
- 2.1.c** What is the age of the oldest adult participant?
75.0
- 2.2** Will there be any minor participants?
No
- 2.3** Will there be any emancipated minor participants?
No
- 2.7** Do you plan to recruit/enroll non-English speaking people?
No
- 2.8** Do you propose to enroll any of the following in this study as participants?

- Employee of the PI or employee of a research team member
 - Individual supervised by PI or supervised by member of research team
 - Individual subordinate to the PI or subordinate to any member of the research team
 - Student or trainee under the direction of the PI or under the direction of a member of the research team
- No
- 2.9 Is this project about pregnant women?
No
- 2.10 Will this project involve fetuses?
No
- 2.11 Does this project involve the use of fetal tissue from any source?
No
- 2.12 Does this project recruit adult participants who may be incompetent or have limited decision-making capacity on initial enrollment into the study?
No
- 2.13 Does this project involve prisoners as participants?
No

3. Performance Sites

- 3.1 Indicate type of site(s) where research will occur (check all that apply):
- Academic Institution
 - Other - Online
- 3.2 Where will project procedures take place (check all that apply)?
- School of Medicine
 - Other WUSTL campus site - Division of General Medical Sciences in the School of Medicine, Health Communication Research Laboratory at Brown School of Social Work
- 3.3 Is this project also being conducted by other researchers at their own sites (e.g. a multi-site collaborative project)?
No

5. Privacy & Confidentiality

- 5.1 Indicate your plans to protect the privacy interests of the participants during the conduct of the study (check all that apply):
- Only the minimum necessary private information is collected for the purposes of the study
 - Any procedures or interventions conducted as part of the study will be conducted in private setting to the extent possible

- Recruitment/consent will occur in a private setting
- Participants will be able to ask questions in a private setting

5.2 Are you collecting or using the Social Security Number of any participants for any purpose?

Yes

5.2.a Provide the intended usage of SSN:

- To provide compensation to participants

5.3 Project uses paper or hard copy consents, surveys, data collection forms, research subject binders, or other hard copy materials (check all that apply):

Yes

- All materials are stored in secured environment
- Access is limited to research team members only

5.4 Project collects, stores and/or transmits electronic data on mobile devices, desktop computers, servers including cloud servers, email, or any other information in electronic form (check all that apply):

Yes

- Access is limited to research team only
- Transmitted using recognized security for electronic submission

5.5 Project collects or uses biologic specimens (check all that apply):

No

5.6 Identify any additional protections in place for data and or samples (check all that apply):

- Formal research staff training process

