- DO NOT include information on studies not proposed in this application.
- Use LAY terminology only. This must be easily understandable by IRB community members and nonscientists.
- DO NOT cut and paste technical abstracts from source of support applications that may not be understood by a general audience.

This is a web-based pilot study examining the effects of narratives about colorectal cancer screeners on intentions and steps to colorectal cancer screening (CRCS) among average-risk adults who are non-adherent to CRCS guidelines (pre-test study IRB# 201405069). Potential participants will complete a brief eligibility survey by phone or online then be invited to participate in the study. Eligible, consented participants will complete a baseline survey and read basic CRCS information then be randomly assigned within the website program to either 1) proceed directly to the post-intervention survey or 2) view a portrait and read a narrative from an individual who got a colonoscopy and either did (“survivor”) or did not (“screener”) have cancer, before completing the post-intervention survey. Narratives will be written as first-person testimonials based on similar stories posted online. Photos will be tailored to the participant (age group, gender, race/ethnicity). One month later, participants will be contacted to complete the follow-up survey online or by phone. A subset of these participants will be contacted for a three month follow-up survey online or by phone.

1.4 Specify your research question(s), study aims or hypotheses:

Aim 1. Examine the direct effect of narratives on intentions and steps to CRCS behavior.

Hypothesis 1: Narratives (vs. Information-only) will increase CRCS intentions and steps to behavior.

Hypothesis 2: Screener (vs. survivor) narratives will increase CRCS intentions and steps to behavior.

Aim 2. Examine mediators of narratives’ effects on intentions and steps to CRCS behavior.

Hypothesis 3: Screener (vs. survivor) narratives will produce greater identification and self-efficacy and less negative affect and counterarguing (mediators) to indirectly influence CRCS intentions and steps to CRCS.

Hypothesis 4: Survivor (vs. screener) narratives will produce greater perceptions of susceptibility to CRC, prevalence of CRC, social norms for CRCS, and negative affect, counterarguing (mediators) to indirectly influence CRCS intentions and steps to CRCS.

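### Apart from baseline intention in the intention models, covariates are chosen by chance baseline imbalance; the steps-to-screening models have no fixed covariate at all

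*Combined protocol and SAP*

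**What the plan says.** Section 1.22 sets one general rule for covariates: "Participants assigned to study arms are expected to be equivalent on baseline measures; any differences will be included as covariates in analyses". It gives no test, threshold or candidate list.

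One covariate is fixed in advance, for one outcome: "Baseline intention will be included as a covariate of later intention".

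The form of the Aim 1 model is left open: "we will conduct analyses of variance or covariance in SPSS, as appropriate".

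Steps to CRCS come under the same aim: "We will also examine steps to CRCS (e.g., using or seeking CRCS information, discussing CRCS with others) as important intermediate outcomes of CRCS adherence". No covariate is named for them, although section 1.4 puts them beside intention in Hypothesis 1 ("Narratives (vs. Information-only) will increase CRCS intentions and steps to behavior") and again in Hypothesis 2.

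No other text supplies an adjustment list. The individual characteristics in Aim 3 enter as exploratory interaction terms, and the post-intervention variables in Aim 2 are mediators. Assignment is random within the website program, and no stratification factors are stated.

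**The concern.** Under randomisation, a baseline difference between arms is a chance event. It carries no information on whether the variable is related to the outcome. A variable that predicts the outcome improves precision whether or not it is imbalanced, and one that does not predict it is of no use even when it is. Selecting on imbalance therefore omits useful adjusters most of the time and admits useless ones at random.

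Two things are at stake. The first is precision, mainly for steps, where baseline intention enters only if the arms happen to differ on it. The second is pre-specification. With no definition of a difference, the Aim 1 model is settled only after the arms have been compared, and the analyst decides what counts.

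**Working it through.** **The plan's own power figure.** Section 1.23 claims more than 80% power for a 0.3 difference, SD 1.0, 120 per condition, p<0.05. The normal approximation is power = Φ(δ / [SD·√(2/n)] − 1.96). With n = 120 this gives 64.2% two-sided; the one-sided figure is 75.1%. Reaching 80% two-sided at 120 per arm would need a covariate correlated at about .56 with the outcome, and the section states none. That shortfall is a separate issue. Here it shows only that the power statement does not settle the adjustment question.

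**Inputs from the documents.** Difference 0.3 and SD 1.0 (section 1.23), three equal arms, and 400 participants with complete data, so 400/3 ≈ 133 per arm at follow-up; 500/3 ≈ 167 per arm as recruited.

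**Assumptions (not in the documents).** A difference means p<.05. Steps are a continuous score with a 0.3 SD effect. The correlation r between baseline intention and steps is .2 to .5. Age group, gender and race/ethnicity together explain 2% of variance (1% and 3% in the intention runs). For intention, baseline and later scores correlate at .6.

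**How often the rule adjusts.** Any one variable is flagged in about 5% of trials. For k independent variables, the chance that at least one is flagged is 1 − 0.95^k: 18.5% for 4, 23% for 5, 40% for 10 and 64% for 20. In simulation, baseline intention entered in 4.9% of trials and any of the four covariates in 18.8%.

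**Steps, screener v survivor, closed form.** Adjusting for baseline intention alone multiplies the SD by √(1 − r²). At 133 per arm, √(2/133) = 0.1226:

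- no adjustment: Φ(0.3/0.1226 − 1.96) = Φ(0.486) = 69%
- r = .3: SD 0.954, Φ(2.564 − 1.96) = 73%
- r = .5: SD 0.866, Φ(2.825 − 1.96) = 81%

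**Steps, simulation.** 10,000 three-arm trials per r, 133 per arm, two-sided 5%. The imbalance rule uses an F test for baseline intention and chi-square tests for the demographics.

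| r | Imbalance rule, p<.05 | Imbalance rule, p<.20 | Fixed set | Gain over p<.05 rule (points) |
|---|---|---|---|---|
| .2 | 67.8% | 68.3% | 70.3% | 2.5 |
| .3 | 68.1% | 68.7% | 72.6% | 4.5 |
| .4 | 68.0% | 69.8% | 76.2% | 8.2 |
| .5 | 68.5% | 70.6% | 80.6% | 12.1 |

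Power under the p<.05 rule hardly moves as the covariate becomes more predictive, because the covariate is left out in about 95% of trials. A repeat simulation gave 68/69/69/69% under the rule, 70/75/77/81% with the fixed set, and 69/73/76/80% with baseline intention alone. Almost all of the gain therefore comes from baseline intention.

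**Steps as yes/no.** For 40% v 55% (5,000 trials), the rule gives 70.5% and the fixed set 72.0% at latent r = .3; at r = .5 the figures are 71.1% and 76.7%.

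**Intention.** Plan (baseline intention plus the rule) v fixed set, 4,000 trials per setting, demographics explaining 1% and 3%:

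- 167 per arm: 93.2 v 93.6% and 92.8 v 93.6%
- 133 per arm: 86.1 v 86.7% and 86.6 v 87.9%

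A noncentral-t check with baseline intention alone gives 92.7% and 86.1%.

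**Validity.** Under the null (steps, r = .4), type I error is 4.6% with the rule and 4.9% with the fixed set, and estimates are unbiased. As an illustrative worst case for analyst discretion, keeping the smallest p-value across no adjustment and thresholds of .05, .10 and .20 raises type I error to 5.7%.

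**The case against.** The strongest reply is that the main outcome is already handled. Section 1.22 makes intention the main outcome and fixes its likely best covariate, and the loss that remains is about 1 point of power. This stands, and it limits the point mainly to steps.

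Steps are subordinate: section 1.22 says they will also be examined, and section 1.23 claims no power for them. The documents give neither their scoring nor a target effect nor a correlation with baseline intention. The 12-point gain needs r = .5 and a continuous score. At r = .2 to .3 the gain is about 2 to 5 points, and for a yes/no outcome it is 1.5 to 5.6. This also stands, so the size is a range. Even so, both Aim 1 hypotheses include steps, and the plan itself calls intention a necessary determinant of screening behaviour, so a non-zero correlation is its own premise.

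The figures above are for Hypothesis 2. For Hypothesis 1 (133 v 266, 0.3 SD), unadjusted power is already about 80%. Baseline intention raises it to about 82/84/87/90% at r = .2/.3/.4/.5, a smaller gain of about 1.5 to 10 points.

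The demographics add only about 1 point, and their use in tailoring the photos does not show that they predict the outcomes. That is correct; they are cheap, not essential.

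Finally, section 1.22 is a summary and does not say that only imbalanced variables may enter the steps models. But the imbalance rule is the only one it states for those models, and this is the only analysis plan in the documents.

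**Conclusion.** The concern holds. Every covariate in the steps models, and all but baseline intention in the intention models, depends on chance imbalance judged against an undefined threshold. Applied mechanically, the rule is valid; the harm is lost precision and a model that is not fixed in advance. For steps the loss is about 2 to 12 points of power as a continuous score (r = .2 to .5) and about 1.5 to 6 as yes/no (latent r .3 to .5). For intention it is about 1 point. These sizes rest on assumed correlations, an assumed 0.3 SD effect on steps and a p<.05 reading of a difference. The weakness in the rule does not depend on them. The change should be made, but no primary conclusion is shown to be at risk without it.

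**What to change.** In section 1.22, replace the imbalance rule with a fixed covariate list, used in every Aim 1 model whatever balance is observed: baseline intention (for steps as well as intention), age group, gender and race/ethnicity. If a shorter list is preferred, baseline intention in the steps models is the part that matters. Report baseline differences descriptively, and label any model that adds imbalanced variables as a sensitivity analysis.

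The cost is one sentence. Baseline intention is already a planned covariate, and the study summary already requires the three demographics to tailor the photos. The statistical cost is a few degrees of freedom: if the demographics explain nothing, power for intention falls by about 0.2 to 0.4 points.

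### The Aim 2 mediation model states no baseline-intention adjustment for steps to screening, and leaves it unclear for follow-up intention, so indirect effects may be confounded

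*Combined protocol and SAP*

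**What the plan says.** All the relevant text is in section 1.22, read with the hypotheses in 1.4 and the sample-size rationale in 1.23.

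- **Aim 2 model.** "we will examine message elaboration and CRCS determinants as mediators (from the Post-intervention Survey) of the effect of narratives on intentions and behaviors", with the outcomes taken from the follow-up survey. On specification: "We propose to use manifest variables and we will create exogenous dummy variables to compare study groups". The model is meant to be joint: "SEM can parsimoniously evaluate multiple mediators and outcomes in a single model".
- **Outcomes of the indirect effects.** Hypothesis 3 expects screener narratives to "produce greater identification and self-efficacy and less negative affect and counterarguing (mediators) to indirectly influence CRCS intentions and steps to CRCS". Hypothesis 4 names the same two outcomes. Steps are therefore a mediation outcome alongside intention.
- **Covariate rule 1, general.** "Participants assigned to study arms are expected to be equivalent on baseline measures; any differences will be included as covariates in analyses".
- **Covariate rule 2.** "Baseline intention will be included as a covariate of later intention". This sits between the Aim 1 ANOVA/ANCOVA sentence and the Aim 1 planned contrasts.
- **Sample size.** "Assuming 400 participants provide complete data, we can test our conceptual model (Figure 1) using structural equation modeling". Section 1.23 adds power above .80 for paths of .19 or more and indirect effects of .07 or more. Figure 1 is not reproduced in the available text.

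**The concern.** An indirect effect is the product of two paths. Randomisation makes the first (narrative to mediator) unconfounded. It does nothing for the second (mediator to outcome), because nobody is randomised to a level of self-efficacy, perceived norms or susceptibility. A participant who already means to be screened may report higher self-efficacy just after the intervention and also seek more information or discuss screening a month later. Omit baseline intention, and the model credits that shared cause to the mediator. The plan itself treats intention as a precondition of screening behaviour, so a link from baseline intention to later steps is its own premise.

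Neither covariate rule closes the gap. Rule 2 covers intention at most, and whether it carries over into the Aim 2 model is not said. Rule 1 is triggered by differences between arms, whereas this confounding is present when the arms are perfectly balanced.

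At stake is which mechanisms the pilot reports as supported. The tests of condition on outcome (Aim 1) and of condition on mediator are unaffected.

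**Working it through.** **1. The plan's own figure.** For a standardised path, power = Φ(atanh(β)·√(N−3) − 1.96), two-sided at .05.
- N = 400, β = .19: .1923 × 19.92 − 1.96 = 1.87, power .97.
- N = 267 (two narrative arms, 400 × 2/3): .1923 × 16.25 − 1.96 = 1.16, power .88.

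The stated bound of .80 holds for the path. A first path of this size will therefore usually be significant, and whether a false indirect effect is declared depends mainly on the second path.

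**2. Inputs.**
- From the documents: 400 complete cases and a path of .19 (1.23).
- From Hypotheses 3 and 4: seven distinct mediators. These are identification, self-efficacy, negative affect and counterarguing, plus susceptibility, prevalence and norms.
- Assumed, because the documents give no values: correlation of baseline intention with mediator (rM) and with outcome (rY); first path α = .19 to .26, where .26 is about √.07; within-arm correlation between mediators ρ = .3; and 40% yes if steps are scored yes/no.
- The true mediator effect is set to zero throughout.

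**3. Spurious coefficient (continuous outcome).** With k mediators and baseline intention omitted,

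b = rM·rY / [(1 − α²)(1 + (k − 1)ρ)].

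For α = .19, 1 − α² = .9639. For α = .26 it is .9324.

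| k | rM/rY | b (α = .19; .26) | spurious αb |
|---|---|---|---|
| 1 | .1/.3 | .03/.9639 = .031; .03/.9324 = .032 | .006; .008 |
| 1 | .3/.3 | .09/.9639 = .093; .09/.9324 = .097 | .018; .025 |
| 1 | .3/.6 | .18/.9639 = .187; .18/.9324 = .193 | .035; .050 |
| 7 | .3/.6 | divide by 1 + 6 × .3 = 2.8: .067; .069 | .013; .018 |

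**4. How often an inert mediator is declared significant.** Simulation, both paths significant at .05, ranges over α = .19-.26 and N = 267-400. There were 2,000 runs per cell for the continuous outcome and 1,000 for yes/no (logistic, rY on the latent scale). Rates are per mediator, unadjusted.

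| Outcome | k | .1/.3 | .3/.3 | stronger pair |
|---|---|---|---|---|
| Continuous | 1 | 6-10% | 28-46% | 75-96% (.3/.6) |
| Continuous | 4 | 5-6% | 10-15% | 28-45% (.3/.6) |
| Continuous | 7 | about 5% | 7-10% | 14-23% (.3/.6) |
| Yes/no steps | 1 | 6-8% | 20-32% | 28-49% (.3/.4) |
| Yes/no steps | 7 | about 5% | 6-8% | 7-10% (.3/.4) |

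With baseline intention in the outcome equation only, the rate is 4.1-5.8% (continuous) and 3.6-5.9% (yes/no).

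The chance that at least one of seven inert mediators is declared significant (continuous outcome, all seven moved by the narrative) is 39-53% at .3/.3 and 71-90% at .3/.6, against 25-31% after adjustment.

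**5. Does the arm-difference rule help?** One mediator, α = .19, rM = rY = .3, 3,000 runs, adjusting only when the arms differ on baseline intention at p < .05 (about 5% of trials). The false-positive rate moves from 42% to 40% at N = 400 and from 29% to 28% at N = 267. It barely helps.

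**The case against.** **The specification may exist where we cannot see it.** Section 1.22 is a summary. The model is defined by reference to Figure 1, and a path diagram is where exogenous variables are normally drawn. This stands as a limit: the point concerns the written analysis text, which is silent on other covariates and does not exclude them. But the same paragraph names this very covariate for intention, so its absence for steps deserves a line.

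**Follow-up intention is literally a later intention.** It is, and the sentence is not expressly confined to Aim 1. That outcome is therefore only ambiguous. Steps stay uncovered on any reading of the prose.

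**The large percentages do not describe the plan.** Largely right. The plan fits several mediators together, so single-mediator rates are an upper illustration, and rY = .6 suits follow-up intention better than steps. For yes/no steps with seven mediators, the per-mediator rate reaches at most 10%. With ten (the text also mentions elaboration, worry and defences), it falls to 4-5%, 5-6% and 6-7% across the three pairs (α = .19). The mediator count is not fixed in the analysis text, however.

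**Much of the any-of-seven figure is multiplicity.** Also right: 25-31% remains after adjustment. If the narrative moves only three of the seven, the figure at .3/.3 is 18-25%, against about 15% adjusted (continuous, α = .19).

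**Reactions to an unread story may hardly correlate with baseline intention.** This is plausible for identification and counterarguing, and then the bias is small.

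**The spurious products lie below the .07 in section 1.23.** True in the step 3 table, but that is no safeguard. A spurious product of about .018 was significant in roughly 42-44% of single-mediator trials at N = 400 (α = .19).

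**Conclusion.** The concern holds. As written, the Aim 2 analysis gives no baseline-intention adjustment for steps and leaves it unclear for follow-up intention, and the arm-difference rule does not address mediator-outcome confounding.

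The direction of the problem is firm but its size is not, because every correlation used is an assumption. It is negligible at .1/.3 with seven mediators. For yes/no steps with seven mediators it is modest, at 6-10% per mediator for .3/.3 to .3/.4. It becomes serious when few mediators are modelled or when baseline intention strongly predicts a continuous outcome. The return to about 5% after adjustment assumes that baseline intention is the only confounder; otherwise adjustment reduces the bias without removing it.

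This should be changed, with medium confidence, mainly because the remedy is nearly free. It does not threaten the Aim 1 comparisons.

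**What to change.** State in the Aim 2 part of section 1.22 that baseline intention enters the Mplus model as a covariate in every outcome equation: follow-up intention and each steps or behaviour outcome, whether or not the arms differ on it. Where the Baseline survey also measures a determinant used as a mediator, add its baseline value too; the survey's contents are not in the available text, so this part is conditional. Paths from baseline intention to the mediators are optional. They help precision and model fit but are not needed to remove this bias. If Figure 1 already shows these paths, the text should say so.

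The cost is one or two sentences and a few degrees of freedom. Baseline intention is already to be collected, so no new data are needed. Because other confounders may remain, the report should describe the indirect effects as resting on no further unmeasured mediator-outcome confounding.

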- What participants will be asked to do/what happens in the study (in sequential order)
- The time period over which procedures will occur
- Long-term follow-up and how it occurs

Participants will complete a baseline web-based survey and read basic CRCS information then, be randomly assigned within the website program to either 1) proceed directly to the post-intervention survey or 2) view a portrait and read a narrative of an individual who got a colonoscopy and either did (“survivor”) or did not (“screener”) have cancer, before completing the post-intervention survey. Interested participants without access to a computer may schedule a time to come to our office to complete the surveys on a study computer, otherwise participants can complete the study anywhere they have access to a computer and internet connection. This session will not exceed 30 minutes and participants will be paid \$20 for their time. One month later, participants will be contacted to complete a follow-up survey online or by phone. This one-month follow-up session will not exceed 10 minutes and participants will be paid \$10 for their time. A subset of participants may complete a six-month and twelve-month follow-up survey. Each of these additional follow-up sessions will not exceed 10 minutes and participants will be paid \$5 for their time.

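### Section 1.23 claims more than 80% power for survivor vs. screener (Hypothesis 2) at 120 per condition; its own inputs give 64% two-sided or 75% one-sided

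*Combined protocol and SAP*

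**What the plan says.** Section 1.23 bases the sample size on intention measured in the post-intervention survey, "assuming a mean score of 3.5 and a standard deviation of 1.0 on a 1-5 scale". From this it claims ">80% power to detect a 0.3 mean difference between survivor vs. screener narratives (Hyp2) with a sample size of 360 (120 per condition") at the 0.05 level. The next sentence draws the recruitment target from that claim: "Thus, we propose to recruit 500 participants (~167 per condition"), with the excess over 360 meant to cover loss to follow-up of under 20%.

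Section 1.22 defines the tests. "Planned contrasts will compare (1) the information only vs. the pooled narrative conditions, and (2) survivor vs. screener narratives". It also says "Baseline intention will be included as a covariate of later intention". Section 1.4 words Hypothesis 2 directionally ("Screener (vs. survivor) narratives will increase CRCS intentions and steps to behavior"), but neither 1.22 nor 1.23 says whether the test is one-sided or two-sided. No baseline/post correlation and no residual SD appear anywhere in the document.

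**The concern.** Section 1.23 gives the difference, the SD, the group size and the significance level, so the power can be recomputed directly. A standardised difference of 0.3 usually needs roughly 175 per group for 80% power two-sided, and 120 is well short of that. Only 240 of the 360 participants enter the Hypothesis 2 contrast, because the information-only condition plays no part in the difference being tested.

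This is the only between-condition contrast for which the plan states a power. It concerns the main outcome, and the recruitment target is presented as following from it. Someone interpreting a null Hypothesis 2 result would credit the comparison with at least 80% power for a difference of 0.30 at 120 per condition. Without adjustment, the difference detectable with 80% power at that size is 0.36 two-sided.

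**Working it through.** **Inputs.**
- Section 1.23: difference 0.3, SD 1.0, n = 120 per condition, α = 0.05, stated power above 80%; proposed recruitment 500, about 167 per condition.
- Section 1.22: Hypothesis 2 is survivor against screener, one condition against one condition; baseline intention is a covariate.
- Not given: sidedness and baseline/post correlation r. Both sidednesses are shown, and every value of r below is an assumption.

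**Step 1: the plan's figure at its own inputs.** The standardised difference is d = 0.3/1.0 = 0.3. The noncentrality is d × √(n/2) = 0.3 × √60 = 2.324.
- Normal approximation, two-sided: Φ(2.324 − 1.960) = Φ(0.364) = 64.2%.
- Normal approximation, one-sided: Φ(2.324 − 1.645) = Φ(0.679) = 75.1%.
- Noncentral t, 238 df: 63.9% two-sided, 74.9% one-sided. Using the three-condition error term (357 df) gives 64.0% two-sided.
- Simulation with means 3.5 and 3.8 and SD 1.0 (40,000 runs): 63.7% two-sided, 74.9% one-sided.

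The stated figure of more than 80% is not reproduced.

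**Step 2: what 80% would take** (noncentral t).

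| | Two-sided | One-sided |
|---|---|---|
| n per condition for 80% | 176 (80.1%; 175 gives 79.9%) | 139 (80.2%; 138 gives 79.98%) |
| Difference with 80% power at n = 120 | 0.36 | 0.32 |

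**Step 3: other readings that might yield the figure.**
- All 360 in two groups of 180: 81% two-sided. This matches, but contradicts the 120 per condition in the same sentence. A two-group total spread over three conditions is a possible origin of the error; that is an inference, and nothing here depends on it.
- Pooled narratives against information only (240 vs 120): 76% two-sided, 85% one-sided. This is Hypothesis 1, whereas the sentence names Hypothesis 2.
- Three-group omnibus F test with a largest difference of 0.3: 53% to 66%, depending on the position of the middle mean.

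**Step 4: the planned covariate.** If 1.0 is the raw SD, adjustment reduces the residual SD to √(1 − r²), so the effective difference is 0.3/√(1 − r²), with 2n − 3 df.

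| Assumed r | n = 120, two-sided | n = 120, one-sided | n = 167, two-sided | n = 167, one-sided |
|---|---|---|---|---|
| Unadjusted | 64% | 75% | 78% | 86% |
| 0.3 | 68% | 78% | 82% | 89% |
| 0.5 | 76% | 85% | 88% | 94% |
| 0.6 | 82% | 89% | 93% | 96% |
| 0.7 | 90% | 95% | 97% | 99% |

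The correlation at which power reaches 80% is 0.56 two-sided and 0.36 one-sided at 120 per condition, and 0.22 two-sided at 167. If 1.0 is already the residual SD, the unadjusted row applies whatever r is.

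**Step 5: the proposed size.** At 167 per condition the noncentrality is 0.3 × √83.5 = 2.741, which gives 78.0% two-sided and 86.2% one-sided. The difference detectable with 80% power is 0.31 two-sided.

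**The case against.** The best defence is the covariate. The 64% and 75% describe an unadjusted comparison, whereas section 1.22 plans to adjust for baseline intention. Baseline and post-intervention intention are collected in one sitting (section 1.13: "This session will not exceed 30 minutes"), so a correlation of 0.6 or 0.7 cannot be ruled out, and at those values 120 per condition gives 82% or 90% two-sided. This stands as a limit on the conclusion: the power of the planned analysis is unknown, not shown to be 64%. It does not rescue the sentence, because 1.23 gives no correlation and states the SD beside the mean score, which reads most naturally as a raw SD. A power claim that needs an unstated input is not supported by the inputs it lists.

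A one-sided reading, which the directional hypothesis might suggest, still gives only 75% unadjusted.

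The practical effect is also modest. The main outcome is measured in the randomisation session, before follow-up losses, so about 167 per condition should largely be available and unadjusted two-sided power is only about 2 points short of 80%. Section 2.1.a expects 600 adults to consent or enrol; if all were randomised equally (an assumption), 200 per condition would give 85% two-sided unadjusted. The study is described as a pilot. All of this bears on severity and is accepted; none of it makes the stated figure correct.

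**Conclusion.** The concern holds. From the inputs in section 1.23, power for Hypothesis 2 at 120 per condition is 64% two-sided or 75% one-sided, about 16 or 5 percentage points below the 80% that the plan says is exceeded. This assumes equal groups, a common SD of 1.0 and no covariate gain. With the planned adjustment and 1.0 as the raw SD, the claim would be true two-sided only for r of about 0.56 or more (0.36 one-sided), and the document offers no value.

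The conclusion is confined to that statement. It does not show that 500 is too few, and the separate structural equation power statement at 400 completers is unaffected. It should be fixed because the sentence is the stated basis for the recruitment target; it does not call the trial into question.

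**What to change.** In section 1.23:
- Remove the claim that 360 (120 per condition) gives more than 80% power.
- State whether the test is one-sided or two-sided, and whether 1.0 is the raw or the residual SD.
- Restate power for the same-session post-intervention intention at about 167 per condition. If two-sided, this is 78% unadjusted, with 80% power for a difference of 0.31. Give alongside it the planned covariance analysis over a range of correlations (82% at 0.3, 88% at 0.5 and, optionally, 93% at 0.6), labelled as assumptions unless data are cited for them.
- Reword the link to the following sentence, so that 500 is justified by the restated figure. It would also help to say how the 600 in section 2.1.a relates to the 500.

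The cost is a short rewording and a less favourable stated power. Enrolment, design and analysis do not change.
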